## **8.0 Patient Disposition**

The number of subjects for each of the following categories will be summarized overall and by country and site:

- Subjects enrolled
- Subjects received at least one dose of study drug
- Subjects who prematurely discontinued study drug
- Subjects who completed study drug
- Subjects who prematurely discontinued the study
- Subjects who completed the study
- Subjects enrolled in first month of RSV season (November)
- Subjects enrolled in second month of RSV season (December)
- Subjects enrolled in third month of RSV season (January)

For the ITT set, the number and percentage of subjects who discontinued study drug or who discontinued from the study, respectively, will be summarized by reason (primary or secondary) and by primary reason.

Furthermore, the following information will be summarized for the ITT set:

- Number of patients observed per visit (*also broken down by enrollment month*)
- Protocol deviations (four major ICH deviations)

- Inclusion/exclusion criteria met [yes, no] based on the inclusion/exclusion module of the CRF
- Specification of violated inclusion/exclusion criteria based on the inclusion/exclusion module of the CRF
- Subject developed withdrawal criteria but was not withdrawn [yes, no]
- Subject received wrong treatment or incorrect dose [yes, no]
- Subject received excluded concomitant treatment during the treatment with palivizumab [yes, no]

## 9.0 Study Drug Exposure and Compliance

Exposure and compliance will be analyzed for the safety set (which is identical to the ITT set).

### Exposure

- Number of doses administered (*continuous and categorical, also broken down by enrollment month; subjects who received an extra dose of study drug due to cardiac surgery are shown separately in this breakdown*)
- Total volume injected [ml] (*per visit and total during study, also broken down by enrollment month; subjects who received an extra dose of study drug due to cardiac surgery are shown separately in this breakdown*)
- Total dose of palivizumab [mg] (*per visit and total during study*) calculated as volume injected [ml] \* 100 [mg/ml] (*also broken down by enrollment month; subjects who received an extra dose of study drug due to cardiac surgery are shown separately in this breakdown*)
- Duration of exposure [days] calculated as the time from first injection to last injection of study drug + 100 days. In addition to the analysis as continuous endpoint, duration of exposure will be analyzed in the following exclusive duration intervals: 101 – 130, 131 – 160, 161 – 190, 191 – 220, > 220 days. (*also broken down by enrollment month; subjects who received an extra dose of study drug due to cardiac surgery are shown separately in this breakdown*)

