5.5 Treatments

Subjects will receive 15 mg/kg palivizumab administered by IM injection every 30 days for a total of at least 3 doses and a maximum of 5 monthly doses except children who undergo cardiac surgery with cardiopulmonary bypass who will receive 6 doses as described below. Following enrollment into the study and the initial injection of palivizumab at Visit 1, subjects will return to the site for visit assessments and palivizumab injections at Days 30 (-5 days), 60 (± 5 days), and if applicable, Days 90 (± 5 days) and 120 (± 5 days).

The total number of individual palivizumab injections will be determined by the time of enrollment into the study shown in [Table 1](#).

Subjects who develop RSV infection should continue to receive monthly doses of palivizumab throughout the RSV season up to a maximum of 5 palivizumab injections.

Subjects who undergo cardiac surgery with cardiopulmonary bypass during their Prophylaxis Period should receive one additional injection of Synagis[®] (Palivizumab) IM 15 mg/kg as soon as possible following completion of the surgery. The date and time when the subject is assessed medically stable for an IM injection should be determined by the Investigator/designee. Any subsequent doses of study drug will continue to be given according to the initial protocol-specified monthly dosing schedule.

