5.5.4 Selection and Timing of Dose for Each Subject

All subjects will receive palivizumab 15 mg/kg IM every 30 days. A ± 5 -day allowance window is permitted, except for the Visit 2 (Day 30), where only -5 -day window is allowed. Subjects will receive at least 3 and a maximum of 5 monthly injections of palivizumab during the 2016 – 2017 RSV season. Palivizumab may be administered at any time during the visit day. All study visit assessments must be performed prior to palivizumab IM injection. Vital signs will be measured before dosing and 30 min after study drug injection. The Investigator/designee will check for any AEs after study drug injection at the visit.

The number of individual doses is determined by the month of enrollment in [Table 1](#).

Table 1. Subject Dosing Timeline

November 2016	December 2016	January 2017	February 2017	March 2017	Total Doses ^a
Visit 1	Visit 2	Visit 3	Visit 4	Visit 5	5
	Visit 1	Visit 2	Visit 3	Visit 4	4
		Visit 1	Visit 2	Visit 3	3

a. An extra dose of palivizumab will be administered in the event of a cardiac surgery with cardiopulmonary bypass surgery.

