8.1.5 Study Drug Exposure

The number and percentage of subjects receiving 1, 2, 3, 4, 5 and more than 5 doses of study drug will be calculated.

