Appendix C. Study Activities

Activity	Visit 1 Enrollment	Visit 2	Visit 3	Visit 4 ^a	Visit 5 ^b /ET	Follow-Up Contact 1 ^c	Follow-Up Contact 2 ^c
Timelines and Allowance Window^d	Day 0 Baseline	Day 30 (-5 Days)	Day 60 (±5 Days)	Day 90 (±5 Days)	Day 120 (±5 Days)	Last Prophylaxis Visit + 30 Days (+5 Days)	Last Prophylaxis Visit + 100 Days (+5 Days)
Informed Consent	X						
Provide subject card	X						
Medical and Birth History	X						
Prior ^e /Concomitant Medication	X	X	X	X	X	X	X
In-/Exclusion Criteria	X						
Assignment of Subject Number	X						
Demographics and Social History	X						
Physical Examination & Weight	X	X	X	X	X		
Body Length/Height	X						
Vital Signs ^f (HR, BP, RR, T°C)	X	X	X	X	X		
Monitor Adverse Events ^g	X ^g	X	X	X	X	X	X
Study Drug administration ^h	X ^h	X	X	X	X		
RSV Diagnostic Test ⁱ							
Assessment of RSV-Hospitalizations		X	X	X	X	X	X

ET = Early Termination

- a. Only applicable to subjects enrolled during November 2016 through December 2016.
- b. Only applicable to subjects enrolled during November 2016.

- c. Telephone contact by Investigator/designee.
- d. Allowance window is given in parentheses.
- e. Will be collected for medications given 2 weeks prior to enrollment.
- f. Vital signs to be measured prior to and 30 minutes after administration of study drug.
- g. SAEs to be registered from the time the study informed consent is signed.
- h. Only applicable to subjects fulfilling Inclusion/Exclusion Criteria.
- i. In case of a cardiac/respiratory hospitalization or deterioration in cardiac/respiratory status in a hospitalized infant, an RSV diagnostic test will be done as soon as possible, but not later than 48 hours of hospitalization.

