## **5.0 Analysis Populations**

### **5.1 Definition of Analysis Populations**

All analyses will be performed on the intent-to-treat (ITT) set, defined as all enrolled subjects who received at least one dose of study drug, unless otherwise indicated.

The safety analyses will be performed on the safety set which is identical to the ITT set.

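### As written, the exposure-duration intervals have no cell for a one-dose child, and their cut points sit on the nominal 3-, 4- and 5-dose durations

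*SAP*

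**What the plan says.** SAP 9.0 (Exposure) defines "Duration of exposure [days] calculated as the time from first injection to last injection of study drug + 100 days". It summarises this as a continuous variable and also in the intervals "101 – 130, 131 – 160, 161 – 190, 191 – 220, > 220 days", with a breakdown by enrollment month. Children given an extra injection because of cardiac surgery are shown separately in that breakdown.

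The table is produced on the safety set. SAP 5.1 makes that set identical to the ITT set, "defined as all enrolled subjects who received at least one dose of study drug", so a child with one injection belongs in it. The protocol foresees such children in section 8.1.5: "The number and percentage of subjects receiving 1, 2, 3, 4, 5 and more than 5 doses of study drug will be calculated".

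Protocol Appendix C labels the first injection visit "Day 0 Baseline" and places the later ones at Days 30, 60, 90 and 120. Protocol 5.5.4 allows ±5 days around each, "except for the Visit 2 (Day 30), where only -5 -day window is allowed". Protocol Table 1 fixes the planned number of injections by enrollment month: 5 for November, 4 for December, 3 for January.

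**The concern.** There are two separate problems.

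First, the formula and the interval list do not fit together at the bottom end. If the smallest value the formula can produce lies below the first interval, a child who stops after one injection is in the denominator but in no row.

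Second, the cut points coincide with the durations that the dosing schedule itself produces. A visit a day or more off target, still inside the protocol window, can move a child to the next row. January enrollees who all received their 3 planned injections on permitted days could then appear in two duration rows, and a reader might take this for a difference in exposure.

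**Working it through.** **Inputs.** Formula and intervals: SAP 9.0. Permitted injection days, counted from Day 0: Visit 2, 25–30; Visit 3, 55–65; Visit 4, 85–95; Visit 5, 115–125 (Protocol 5.5, 5.5.4 and Appendix C). Assumed: no missed injections and no extra injection after surgery, whose date the schedule does not fix.

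**Smallest value.** The lowest duration the SAP covers is 101 days. With one injection, first and last dates are the same:

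- As written: 0 + 100 = 100 days, in no interval.
- With an inclusive count: 0 + 1 + 100 = 101 days, in 101–130.

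Only the inclusive count reproduces the SAP's lower limit.

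**As written: duration = (last − first) + 100.**

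| Doses | Nominal | Permitted range | Permitted days per interval |
|---|---|---|---|
| 1 | 100 | 100 | none |
| 2 | 130 | 125–130 | 6 in 101–130 |
| 3 | 160 | 155–165 | 6 in 131–160, 5 in 161–190 |
| 4 | 190 | 185–195 | 6 in 161–190, 5 in 191–220 |
| 5 | 220 | 215–225 | 6 in 191–220, 5 in >220 |

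The 2-dose group is not split, because Visit 2 may only be early.

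**Inclusive: duration = (last − first) + 1 + 100.**

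| Doses | Nominal | Permitted range | Permitted days per interval |
|---|---|---|---|
| 1 | 101 | 101 | 1 in 101–130 |
| 2 | 131 | 126–131 | 5 in 101–130, 1 in 131–160 |
| 3 | 161 | 156–166 | 5 in 131–160, 6 in 161–190 |
| 4 | 191 | 186–196 | 5 in 161–190, 6 in 191–220 |
| 5 | 221 | 216–226 | 5 in 191–220, 6 in >220 |

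The +1 gives the one-dose child a cell but leaves the 3-, 4- and 5-dose groups split and splits the 2-dose group as well.

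**Sensitivity to the visit target.** SAP Table 1 uses nominal RxDAY 30, 60, 90 and 120, where the first dose is RxDAY 1. Taking these as targets reduces elapsed time by one day. Without +1, nominal durations for 3, 4 and 5 doses become 159, 189 and 219, and the split is 7 and 4 permitted days. With +1 they return to 160, 190 and 220, and the split is 6 and 5. These groups are split in all four combinations.

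**Recut, using the written formula.** The midpoints between 100, 130, 160, 190 and 220 are 115, 145, 175 and 205, which gives 100–114, 115–144, 145–174, 175–204 and ≥205. The permitted ranges 100, 125–130, 155–165, 185–195 and 215–225 then each fall in one interval. The SAP Table 1 windows end at RxDAY 45, 75 and 105, which are 44, 74 and 104 elapsed days, so durations of 144, 174 and 204. The upper three cuts therefore match Table 1. The 114/115 cut has no counterpart there, because the Day 30 window starts at RxDAY 2.

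**The case against.** The strongest reply is that the count was meant to be inclusive. SAP 6.0 describes RxDAY as a number of days between two dates and then computes it with +1, and an interval list that starts at 101 fits the same habit. On that reading the nominal durations for 1 to 5 doses are 101, 131, 161, 191 and 221, which are the lower limits of the five intervals. This is probably what the authors had in mind, so a reader should not infer that a one-dose child is certain to be lost from the table. What stands is that the +1 is written for RxDAY and not here, and a programmer who follows the text gets 100.

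The second reply is that duration is measured in days and any fixed cut separates some children. A reader might infer that the intervals are meant to represent dose count and fail at it. No passage says so. SAP 9.0 reports number of doses, volume and milligrams separately, gives duration as a continuous variable, and calculates the actual days from first dose to each injection. A one-dose child would still appear in those summaries. This limits the consequence. It does not make the present cuts a good choice, since they lie exactly where on-schedule children fall.

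A reader might also infer that about half of compliant children would land one row away from the rest. That needs last visits spread evenly over the 11 permitted days (5/11 = 45% in the upper interval as written). The documents give no distribution of visit timing. The share could be 0% if every last visit is on or before its nominal day, or 100% if every one is late.

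**Conclusion.** The point holds as a minor one, in two parts of different strength. The missing one-dose cell follows from the formula as written and disappears under an inclusive count; it matters only if some child stops after one injection. The splitting of the 3-, 4- and 5-dose groups does not depend on the counting rule: 6 and 5 permitted days as written, 5 and 6 with +1. These figures count permitted days and do not predict how many children will fall in each row. They assume scheduled injections only, all within window. The effect is confined to one descriptive exposure table and its breakdown by enrollment month. The primary endpoint and the adverse event windows do not use this variable.

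**What to change.** State the day count explicitly and move the cuts midway between the nominal durations. Suggested text: duration of exposure = date of last injection − date of first injection + 100 days, tabulated as 100–114, 115–144, 145–174, 175–204 and ≥205 days.

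If the current intervals are kept, write the +1 into the formula so that a one-dose child falls in 101–130. This closes the gap but does not remove the splitting, and a table footnote should then say that children with the same dose count may fall in adjacent intervals because of permitted visit timing.

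The cost is a sentence of SAP wording and one format statement. No data collection changes.

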## Compliance

- Compliance with study drug [%] calculated as (number of injections received/number of injections planned) \* 100. *(also broken down by enrollment month; subjects who received an extra dose of study drug due to cardiac surgery are shown separately in this breakdown)* The number of doses planned is calculated based on the month of enrollment and whether the subject completed the study or early discontinued.
- For each visit, the actual number of days between the first dose of study drug and the injection date at that visit will be calculated.

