5.5.6 Treatment Compliance

The investigator or his/her designated and qualified representatives will administer study drug only to subjects enrolled in the study in accordance with the protocol. The study drug must not be used for reasons other than that described in the protocol.

The used vials will be retained by the Investigator or designee after each injection. An exact date of injection will be recorded for each subject. An overall accountability of study drug will be performed and verified by the site and the AbbVie monitor. An explanation will be recorded for any discrepancies.

As long as the study drug is administered solely by the study center personnel, and the subject receives all doses in the defined timelines, the subject will be considered compliant. If any of the applicable doses was missed or administered outside of the allowance window, the subject will be considered non-compliant. Thus, the compliance will only be calculated on the study level (i.e., percentage of subjects, who received all applicable doses within the defined timelines).

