### Definition of Analysis Windows

The following visit windows will be used to assign visit numbers for analysis. If the assigned visit number results in more than one non-missing assessment in a given visit window, then the assessment performed closest to the nominal day will be used in analyses. When more than 1 day is of equal proximity to the nominal day, then the data collected after the nominal day will be used in analyses.

Visit windows depend on when a variable is measured during the study.

RxDAY is defined as the number of days between the day of the first dose of study drug and the day of the time point of interest.

$RxDAY = \text{date of visit} - \text{date of first study drug} + 1.$

RxDAYs are negative values when the time point of interest is prior to the first study drug dose day. RxDAYs are positive values when the time point of interest is on or after the first study drug dose day. The day of the first dose of study drug is defined as RxDAY 1, while the day prior to the first study drug dose is defined as RxDAY -1 (there is no RxDAY 0).

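### SAP 9.0 replaces the protocol's compliance percentage (subjects with every applicable dose in window) with injections received over planned, gives no reason, and never reports the protocol figure

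*SAP*

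**What the plan says.** Protocol 5.5.6 gives each subject a yes/no status: "If any of the applicable doses was missed or administered outside of the allowance window, the subject will be considered non-compliant". It then states that "the compliance will only be calculated on the study level" and defines that figure as the "percentage of subjects, who received all applicable doses within the defined timelines". The windows are in Protocol 5.5, 5.5.4 and Appendix C. A ±5-day "allowance window is permitted, except for the Visit 2 (Day 30"), where only 5 days early is allowed. Appendix C counts the first dose as Day 0, so Visit 2 runs from Day 25 to Day 30.

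SAP 9.0, under Compliance, has two items. The first is "Compliance with study drug [%] calculated as (number of injections received/number of injections planned") × 100, with this rule for the denominator: "The number of doses planned is calculated based on the month of enrollment and whether the subject completed the study or early discontinued". It is broken down by enrollment month, and subjects with an extra surgical dose are shown separately in that breakdown. The second item is that, for each visit, "the actual number of days between the first dose of study drug and the injection date at that visit will be calculated". The SAP introduction presents the document as elaborating the protocol's methods and declares no departure on compliance.

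**The concern.** The two definitions measure different things. The protocol's is all-or-nothing per subject and depends on timing. The SAP's is a dose count with no timing element. The protocol's word *only* makes it hard to read the ratio as a permitted alternative.

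The ratio is also loosely specified. The SAP does not say how early discontinuation changes the number planned, and cardiac surgery is not among the things that determine it. Two programmers could therefore produce different results from the same data.

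What is at stake is one descriptive result. The study report would carry a figure labelled compliance that is not the one the protocol defines and that late injections cannot lower, in a study whose injections follow a 30-day schedule with explicit windows.

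**Working it through.** **Stated figure.** Neither document gives a compliance figure, so there is nothing to reproduce. The check is a comparison of definitions followed by illustrative arithmetic.

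**1. Does any other SAP output give the protocol percentage?**
- *Day counts (SAP 9.0, Compliance).* Days from first dose are calculated for each visit but are not compared with any window.
- *SAP Table 1.* Its purpose is different: "The following visit windows will be used to assign visit numbers for analysis". Its window for scheduled Day 30 is RxDAY 2 to 45. RxDAY adds 1, so a dose 44 days after the first is RxDAY 45. That is inside the SAP window and outside the protocol's Day 25 to 30.
- *Deviations (SAP 8.0).* The four categories cover eligibility, withdrawal criteria, wrong treatment or dose, and excluded concomitant treatment. None names dose timing.
- *Exposure (SAP 9.0).* This covers dose counts, volume, milligrams and duration, with no in-window status.

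No specified output gives the percentage.

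**2. Formulas.**
- SAP, per subject: 100 × injections received / injections planned, averaged here over subjects.
- Protocol, study level: 100 × subjects with every applicable dose given in window / subjects.

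Planned doses are 5, 4 or 3 for November, December or January enrollment (Protocol Table 1), so 4, 3 or 2 doses follow the first. The illustrations use 50 subjects, the planned enrollment. All deviation counts and rates below are assumptions.

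**3. Out-of-window doses only.** Each dose after the first is out of window independently with probability p, enrollment months are equally common, and no dose is missed. The protocol figure is the mean of (1−p)^4, (1−p)^3 and (1−p)^2.

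| p | November | December | January | Protocol, mean | SAP ratio |
|---|---|---|---|---|---|
| 2% | 92.2% | 94.1% | 96.0% | 94.1% | 100% |
| 5% | 81.5% | 85.7% | 90.2% | 85.8% | 100% |
| 10% | 65.6% | 72.9% | 81.0% | 73.2% | 100% |

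**4. Skipped doses.** A continuing subject who skips one dose scores 4/5 = 80%, 3/4 = 75% or 2/3 = 66.7%, so the ratio does respond. If 5 of 50 subjects each skip one of 5 doses:
- SAP: (45 × 100 + 5 × 80)/50 = 98%
- Protocol: 45/50 = 90%

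**5. Early discontinuation.** A November enrollee who stops after 2 doses scores 2/2 = 100% if the plan is cut back at discontinuation, which is the natural reading of the SAP. On the full schedule the score is 2/5 = 40%.

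**6. Extra surgical dose.** If it counts as received but not as planned, a completer scores 6/5 = 120%, 5/4 = 125% or 4/3 = 133.3%. In the overall line such values could offset missed doses.

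**7. Combined illustration.** Of 50 subjects, 5 November enrollees stop after 2 timely doses, 5 completers have one out-of-window dose, and 40 have no deviation.
- SAP, plan cut back at discontinuation: (40 × 100 + 5 × 100 + 5 × 100)/50 = 100%
- SAP ratio on the full enrollment-month plan: (45 × 100 + 5 × 40)/50 = 94%
- Protocol, full schedule applicable: 40/50 = 80%
- Protocol, doses due until discontinuation: 45/50 = 90%

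**8. Direction.** For the same set of applicable doses and without extra doses, a compliant subject scores 100% on the ratio and a non-compliant subject scores at least 0%. The mean ratio therefore cannot be below the protocol percentage, so any discrepancy flatters compliance.

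**The case against.** The strongest reply is that little is lost.

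- *Other outputs.* The SAP reports doses administered by enrollment month with surgical extras shown separately, patients observed per visit, and discontinuations with reasons. Set against Protocol Table 1, these show most of the missed-dose part of the protocol figure. The day counts are calculated too. This stands: what is missing is the in-window flag and the subject percentage built on it. But that percentage is the measure the protocol names, and none of these outputs is it.
- *Early discontinuers.* Making planned doses depend on discontinuation may be the SAP's way of applying the protocol's *applicable*, which the protocol leaves undefined for these subjects. This also stands. It is an ambiguity shared by both documents, and the 100% score for a subject who stops after 2 of 5 doses rests on one reading.
- *Extra dose.* Scores above 100% arise only if the extra dose enters the numerator and not the denominator. The SAP does not settle this, and there may be no such subjects.
- *Rates and consequences.* All rates are assumed, the study is descriptive, and every analysis uses subjects with at least one dose. This is correct. It limits the weight of the point but does not reconcile the two definitions.

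**Conclusion.** The concern holds. SAP 9.0 substitutes a different measure for the one in Protocol 5.5.6, gives no reason, and specifies no output that yields the protocol percentage. That follows from the text and needs no assumed numbers.

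The size depends on deviation rates the documents do not give. Under the assumptions used, the gap from late or early doses alone is about 6, 14 or 27 percentage points (100% against 94.1%, 85.8% or 73.2%). It is 8 points when 5 of 50 subjects each skip one of 5 doses (98% against 90%), and nil when there are no deviations. The undefined denominators for early discontinuers and surgical subjects are secondary, and the first is partly the protocol's own gap. The primary analysis is unaffected. This should be corrected, but it does not threaten the study's conclusions.

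**What to change.** In SAP 9.0, make the Protocol 5.5.6 figure the compliance result: number and percentage of subjects with all applicable doses given inside the protocol allowance windows.

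- Derive it from the days since first dose already calculated, with the first dose as Day 0 as in Appendix C. RxDAY must not be used unshifted: a dose exactly 30 days after the first is RxDAY 31, and because Visit 2 has no positive allowance it would be wrongly classed as late.
- Define *applicable* for early discontinuers. Showing the figure both on the full enrollment-month schedule and on doses due until discontinuation would make the choice visible.
- If the injection ratio is kept, label it supplementary. Preferably base it on the full enrollment-month plan, and treat the extra surgical dose the same way in numerator and denominator in the overall figure.

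The essential change is the first; the dual display and the ratio's denominator are useful additions. The cost is a few sentences of SAP text and one derived variable, with no new data. The reported compliance may be lower than the SAP ratio would have shown.

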#### **4.2 Study Design**

This is a Phase 3b, prospective, multicenter, open-label, non-controlled study of immunoprophylaxis with the intramuscular (IM) administration of palivizumab for the prevention of RSV hospitalizations in infants at high risk. Approximately 50 infants will be enrolled in the study and will receive palivizumab solution for injection at 15 mg/kg by IM injection every 30 days for a minimum of 3 and a maximum of 5 injections given during anticipated periods of RSV risk in the community; the number of doses will depend on the time of enrollment during the RSV season. Prior to each injection of study

drug all enrolled subjects will undergo safety assessment. All subjects that received at least one injection of palivizumab will be followed by a telephone contact at 30 and 100 days after their last injection.

All cardiac/respiratory hospitalizations or deterioration in the cardiac/respiratory status in a hospitalized infant will be evaluated by testing nasopharyngeal specimens with a commercially available licensed RSV diagnostic test (RT-PCR) to determine if RSV contributed to the hospitalization or deterioration.

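### SAP 9.0 counts a bypass replacement injection as received but not as planned, and it omits the compliance percentage that Protocol 5.5.6 specifies

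*SAP*

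**What the plan says.** Under Compliance, SAP 9.0 defines a percentage for each subject from the ratio "number of injections received/number of injections planned". The denominator rule is: "The number of doses planned is calculated based on the month of enrollment and whether the subject completed the study or early discontinued". The same bullet adds a breakdown by enrollment month, and "subjects who received an extra dose of study drug due to cardiac surgery are shown separately in this breakdown". SAP 4.2 says that "the number of doses will depend on the time of enrollment during the RSV season" and does not mention the replacement injection.

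Protocol Table 1 (5.5.4) sets the scheduled doses at 5, 4 and 3 for November, December and January enrollment. Its footnote makes the bypass dose additional to those totals, and Protocol 5.5 keeps the monthly schedule running after surgery.

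Protocol 5.5.6 measures compliance in another way: "If any of the applicable doses was missed or administered outside of the allowance window, the subject will be considered non-compliant". It goes on to say that "compliance will only be calculated on the study level (i.e., percentage of subjects, who received all applicable doses within the defined timelines".

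**The concern.** The numerator and denominator of the SAP ratio do not cover the same injections. The replacement is an injection of study drug, and nothing in SAP 9.0 takes it out of the received count. The planned count has no term for it. Two errors follow, both upward. A bypass child dosed exactly as the protocol asks scores above 100%. A bypass child who missed a scheduled dose can have the gap filled by the replacement and score exactly 100%.

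The second error matters more, because the figure looks normal and contradicts the protocol's classification of that child. No other planned compliance figure would correct it, since the SAP does not include the Protocol 5.5.6 percentage. That omission concerns all of the roughly 50 subjects. A dose-count ratio takes no account of timing, so any child dosed outside the window can also score 100% while being non-compliant under the protocol.

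**Working it through.** **Inputs.** Scheduled doses d = 5, 4, 3 for November, December, January (Protocol Table 1). Replacement dose = 1, additional to d (Table 1 footnote; Protocol 5.5). About 50 subjects (SAP 4.3). All children below are taken to complete the study, because the SAP adjusts planned doses for early discontinuation without giving the rule.

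**The plan's own figure.** One visit per month from the enrollment month through March gives 5, 4 and 3, which matches Table 1. This is the SAP denominator.

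**Per-child results.** Compliance = 100 × received / planned.

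| Child (Nov / Dec / Jan) | SAP as written | Option A: planned = d + 1 | Option B: scheduled injections only |
|---|---|---|---|
| Bypass, all doses given | (d+1)/d = 120.0 / 125.0 / 133.3% | (d+1)/(d+1) = 100% | d/d = 100% |
| Bypass, one scheduled dose missed, replacement given | d/d = 100% | d/(d+1) = 83.3 / 80.0 / 75.0% | (d−1)/d = 80.0 / 75.0 / 66.7% |
| Bypass, all scheduled doses given, replacement missed | d/d = 100% | d/(d+1) = 83.3 / 80.0 / 75.0% | d/d = 100% |
| No bypass, one scheduled dose missed | (d−1)/d = 80.0 / 75.0 / 66.7% | same | same |

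- Row 1 is too high by 100/d = 20.0 / 25.0 / 33.3 points.
- Row 2 is too high by 16.7 / 20.0 / 25.0 points against option A, or 20.0 / 25.0 / 33.3 against option B.
- Row 4 shows that the formula works as intended when there is no replacement injection.

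**Effect on the overall mean.** With the other 49 children at 100%, one fully dosed bypass child adds (100/d)/50 = 0.40 / 0.50 / 0.67 points. The documents give no surgery rate, so any larger count is an assumption. Five such children would add 5 × (100/d)/50 = 2.0 / 2.5 / 3.3 points.

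**The separate display.** It sits inside the enrollment-month breakdown, which the SAP presents as an addition to the main summary, so the overall figure still includes these children. In the separate row the ratio is still computed in the same way. The row holds only children who received an extra dose.

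**The missing measure.** Besides the ratio, the Compliance section of SAP 9.0 plans only the number of days from first dose to each injection. That is raw material for judging the windows in Protocol 5.5.4, but no proportion of subjects with every dose in window is planned.

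**The case against.** The best defense is that little depends on this figure. Compliance defines no analysis set, has no threshold, and is purely descriptive. The SAP foresaw extra-dose children: it separates them in the exposure and compliance breakdowns and displays their vital signs separately. A value of 120% in a row labelled as extra-dose subjects largely explains itself. A missed scheduled dose would still show in the per-visit counts (SAP 8.0) and the injection days (SAP 9.0). All of this stands as an argument about size. It does not make the ratio or the overall summary correct. It is also fair that the SAP never states that the replacement counts as received; that is the plain reading, and nothing excludes it.

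A reader might infer more than the documents support:

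- *Any child with a missed dose scores 100%.* This needs bypass surgery and the replacement injection. Without them the ratio falls to 80%, 75% or 67%.
- *A bypass child who misses only the replacement is also misclassified.* That depends on whether the replacement is an applicable dose under Protocol 5.5.6. It is contingent on the child being stable and has no numerical window, so the documents leave this open.
- *The mean could be off by 2 to 3 points.* That needs five fully dosed bypass children. Five is the whole minimum CHD target in Protocol 5.1, and the upper end needs all five enrolled in January.
- *Protocol 5.5 must be amended.* It says "except children who undergo cardiac surgery with cardiopulmonary bypass who will receive 6 doses as described below", and six is right only for November. But the same section asks for one additional injection, the Table 1 footnote agrees, and the Day 150 limit is in the Synopsis and 5.1. An amendment needing ethics approval would gain little.

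**Conclusion.** The point holds, at small size. As written, the SAP 9.0 ratio gives a bypass completer 20 to 33 points too much when fully dosed. When one scheduled dose is missed and the replacement given, it shows 100% where a consistent ratio gives 67% to 83%. Separately, the SAP leaves out the only compliance measure that Protocol 5.5.6 provides for.

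This rests on Table 1 doses, study completion, and the plain reading that a replacement is an injection received. The shift in the mean, 0.4 to 0.7 points for one fully dosed bypass child, also assumes 50 subjects with all others at 100%. The primary proportion and its exact confidence interval do not depend on compliance and do not change.

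**What to change.** Change SAP 9.0 only.

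1. Make the numerator and denominator match, by one of two rules.
   - *Option A:* add 1 to the planned doses of a subject due a bypass replacement injection. This registers a missed replacement. The SAP must then say who counts as due one, using surgery through Study Day 150 and stability for injection as in Protocol 5.1. The data lists in Protocol 5.3.1 do not name stability as an item, so its availability should be checked first.
   - *Option B:* compute the ratio on scheduled injections only and report replacement injections separately. This needs only the identification of extra doses that the SAP already requires, but it does not register a missed replacement.
2. Add the Protocol 5.5.6 percentage: subjects with every applicable dose given in window, over all subjects in the safety set. Derive it from the recorded injection dates and the Protocol 5.5.4 windows, and state whether a replacement counts as an applicable dose.

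The cost is a few SAP sentences and one more line in the compliance table, before database lock. No new visits or assessments and no protocol amendment are needed.
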